9.2.8. Future Biomedical Research (Optional Use of Samples)

Patients who agree to participate in the future biomedical research sub-study will be required to consent to this optional sub-study before samples are banked in long-term storage. Unused tumor samples for study-related research will be stored for up to 15 years after the final date of the database lock. The unused samples may be utilized for future biomedical research of CSCC and related diseases. No additional samples will be collected for future biomedical research. After 15 years, any residual samples will be destroyed. The results of these future biomedical research analyses will not be presented in the CSR.

9.2.9. Patient Reported Outcomes

Patient reported outcomes will be measured at a frequency indicated in [Table 2](#) and [Table 3](#) using the self-administered EORTC QLQ-C30. The EORTC QLQ-C30 is a validated instrument that assesses HRQoL across multiple domains, including global health status, functioning (physical, role, emotional, cognitive, and social), patient-reported symptom scales (fatigue, nausea and vomiting, pain) and single items (appetite loss, dyspnea, insomnia, constipation, diarrhea, financial impact). Patients will be asked to complete the questionnaire prior to any study procedures being performed during a given study visit.

10. SAFETY DEFINITIONS, REPORTING, AND MONITORING

10.1. Obligations of Investigator

The investigator must promptly report to the Institutional Review Board (IRB)/Ethics Committee (EC) all unanticipated problems involving risks to patients, according to local regulations. This may include death from any cause and all SAEs suspected to be related to the use of the study drug. It is recommended that all other SAEs be reported to the IRB/EC, according to local regulations.

10.2. Obligations of Sponsor

During the course of the study, the sponsor will report in an expedited manner all SAEs that are both unexpected and at least reasonably related to the study drug (suspected unexpected serious adverse reaction [SUSAR]), to the health authorities, ECs/IRBs as appropriate, and to the investigators in a blinded manner.

Any AE not listed as an expected event in the Reference Safety Information section of the Investigator's Brochure will be considered as unexpected.

In addition, the sponsor will report all other SAEs to the health authorities, according to local regulations.

At the completion of the study, the sponsor will report all safety observations made during the conduct of the trial in the clinical study report to health authorities and ECs/IRB as appropriate.

10.3. Definitions

10.3.1. Adverse Event

An AE is any untoward medical occurrence in a patient administered a study drug which may or may not have a causal relationship with the study drug. Therefore, an AE is any unfavorable and unintended sign (including abnormal laboratory finding), symptom, or disease which is temporally associated with the use of a study drug, whether or not considered related to the study drug.

An AE also includes any worsening (ie, any clinically significant change in frequency and/or intensity) of a pre-existing condition that is temporally associated with the use of the study drug.

Progression of underlying malignancy will not be considered as an AE if it is clearly consistent with the typical progression pattern of the underlying cancer (including time course, affected organs, etc). Clinical symptoms of progression may be reported as AEs if the symptom cannot be determined as exclusively due to the progression of the underlying malignancy or does not fit the expected pattern of progression for the disease under study.

If there is any uncertainty about an AE being due only to progression of the underlying malignancy, it should be reported as an AE or as an SAE as outlined in Section 10.3.2.

10.3.2. Serious Adverse Event

An SAE is any untoward medical occurrence that at any dose:

- Results in **death**. Includes all deaths, even those that appear to be completely unrelated to study drug (eg, a car accident in which a patient is a passenger).
- Is **life-threatening**. In the view of the investigator, the patient is at immediate risk of death at the time of the event. This does not include an AE that had it occurred in a more severe form, might have caused death.
- Requires in-patient **hospitalization** or **prolongation of existing hospitalization**. In-patient hospitalization is defined as admission to a hospital or an emergency room for longer than 24 hours. Prolongation of existing hospitalization is defined as a hospital stay that is longer than was originally anticipated for the event or is prolonged due to the development of a new AE as determined by the investigator or treating physician.
- Results in persistent or significant **disability/incapacity** (substantial disruption of one's ability to conduct normal life functions).
- Is a **congenital anomaly/birth defect**
- Is an **important medical event** - Important medical events may not be immediately life-threatening or result in death or hospitalization, but may jeopardize the patient or may require intervention to prevent one of the other serious outcomes listed above (eg, intensive treatment in an emergency room or at home for allergic bronchospasm; blood dyscrasias or convulsions that do not result in hospitalization; or development of drug dependency or drug abuse).

Hospitalization or death due solely to manifestations consistent with typical progression of underlying malignancy will not be considered an SAE.

10.3.3. Adverse Events of Special Interest

An adverse event of special interest (AESI; serious or non-serious) is one of scientific and medical concern specific to the sponsor's product or program, for which ongoing monitoring and rapid communication by the investigator to the sponsor can be appropriate. Such an event might warrant further investigation in order to characterize and understand it. Depending on the nature of the event, rapid communication by the trial sponsor to other parties (eg, regulators) might also be warranted (Section 10.4.3).

10.3.4. Infusion Reactions

Infusion reactions are defined as any relevant AE that occurs during the infusion or within 24 hours after the infusion is completed. All infusion reactions must be reported as AEs (defined in Section 10.4.1) and graded using the grading scales as instructed in Section 10.5.1.

10.4. Recording and Reporting Adverse Events

10.4.1. Adverse Events

The investigator (or designee) will seek information on AEs at each patient contact and record all AEs that occur from the time the informed consent is signed until 90 days after the last dose of study drug. Prior to initiation of study drug, only the following categories of AEs should be reported on the AE eCRF:

- SAEs
- Non-SAEs associated with a protocol-mandated intervention (eg, AEs related to an invasive procedure such as a biopsy)

Other AEs that occur prior to first treatment should be reported on the medical history eCRF.

All AEs after initiation of study drug and until 90 days after the last dose of study drug, regardless of relationship to study drug, will be reported on the AE eCRF. Additionally, any SAE or other AE of concern that the investigator believes may be related to study drug and that occurs later than 90 days after last study drug should be reported.

Information on follow-up for AEs is provided in Section 10.4.6. Laboratory, vital signs, or ECG abnormalities are to be recorded as AEs as outlined in Section 10.4.5.

10.4.2. Serious Adverse Events

All SAEs, regardless of assessment of causal relationship to study drug, must be reported to the sponsor (or designee) within 24 hours.

Information not available at the time of the initial report must be documented in a follow-up report. Substantiating data such as relevant hospital or medical records and diagnostic test reports may also be requested.

In the event the investigator is informed of an SAE that occurs 90 days after the last dose of study drug, only those SAEs or other AEs of concern deemed by the investigator to be related to study drug will be reported to the sponsor. The investigator should make every effort to obtain follow-up information on the outcome of an SAE until the event is considered resolved, chronic and/or stable.

For the purposes of this study, planned resection procedures and associated hospitalization are not considered SAEs.

10.4.3. Other Events that Require Accelerated Reporting to Sponsor

The following events also require reporting to the sponsor (or designee) within 24 hours of learning of the event:

Symptomatic Overdose of Study Drug: Accidental or intentional overdose of at least 2 times the intended dose of study drug within the intended therapeutic window, if associated with an AE.

Pregnancy: Although pregnancy is not considered an AE, it is the responsibility of the investigator to report to the sponsor (or designee), within 24 hours of identification, any pregnancy occurring in a female study patient or female partner of a male study patient, during the study or within 180 days of the last dose of study drug. Any complication of pregnancy affecting a female study patient or female partner of a male study patient, and/or fetus and/or newborn that meets the SAE criteria must be reported as an SAE. Outcome for all pregnancies should be reported to the sponsor.

Adverse Events of Special Interest: All AESI, serious and non-serious, must be reported within 24 hours of identification using the same reporting process as for SAE reporting, per Section 10.4.2. Adverse events of special interest for this study include the following:

- Grade 2 or higher IRRs (Section 8.4)
- Grade 3 or higher irAEs (Section 8.3.3)

10.4.4. Reporting Adverse Events Leading to Withdrawal from the Study

All AEs that lead to a patient's withdrawal from the study must be reported to the sponsor's Medical/Study Director within 30 days.

10.4.5. Abnormal Laboratory, Vital Signs, or Electrocardiogram Results

The criteria for determining whether an abnormal objective test finding should be reported as an AE include:

- The test result is associated with accompanying symptoms, and/or
- The test result requires additional diagnostic testing or medical/surgical intervention, and/or

- The test result leads to a change in dosing (outside of protocol-stipulated dose adjustments), discontinuation from the study, significant additional concomitant drug treatment, or other therapy

Contact the Medical/Study Director in the event the investigator feels that an abnormal test finding should be reported as an AE, although it does not meet any of the above criteria.

Repeating an abnormal test, in the absence of any of the above conditions, does not constitute an AE. Any abnormal test result that is determined to be an error does not require reporting as an AE.

Evaluation of severity of laboratory abnormalities will be assessed according to the scale outlined in Section 10.5.1.

10.4.6. Follow-up

Information for any non-SAE that starts during the treatment period or within 90 days after last treatment will be collected from the time of the event until resolution of the event, or until the patient's last study visit, whichever comes first.

Serious adverse event information will be collected until the event is considered resolved, chronic and/or stable.

10.5. Evaluation of Severity and Causality

10.5.1. Evaluation of Severity

The severity of AEs (including test findings classified as AEs) will be graded using the NCI-CTCAE v5. Adverse events not listed in the NCI-CTCAE v5 will be graded according to the following scale (Table 5):

Table 5: Grading System for Adverse Events Not Listed in NCI-CTCAE

Grade	Severity	Description
1	Mild	Asymptomatic or mild symptoms; clinical or diagnostic observations only; intervention not indicated.
2	Moderate	Minimal, local, or noninvasive intervention indicated; limiting age-appropriate instrumental ADL*.
3	Severe	Severe or medically significant but not immediately life-threatening; hospitalization or prolongation of hospitalization indicated; disabling; limiting self-care ADL**.
4	Life-threatening	Life-threatening consequences; urgent intervention indicated.
5	Death	Death related to AE

* Instrumental Activities of Daily Living (ADL) refer to preparing meals, shopping for groceries or clothes, using the telephone, managing money, etc.

** Self-care ADL refer to bathing, dressing and undressing, feeding self, using the toilet, taking medications, and not bedridden.

10.5.2. Evaluation of Causality

Relationship of Adverse Events to Study Drug:

The relationship of AEs to study drug will be assessed by the investigator and will be a clinical decision based on all available information. The following question will be addressed:

Is there a reasonable possibility that the AE may have been caused by the study drug?

The possible answers are:

- **Not Related:** There is no reasonable possibility that the event may have been caused by the study drug
- **Related:** There is a reasonable possibility that the event may have been caused by the study drug

The investigator should justify the causality assessment of each SAE.

A list of factors to consider when assessing the relationship of AEs to study drug is provided below. Please note that this list is not exhaustive.

Is there a reasonable possibility that the event may have been caused by the study drug?

No:

- due to external causes such as environmental factors or other treatment(s) being administered
- due to the patient's disease state or clinical condition
- do not follow a reasonable temporal sequence following the time of administration of the dose of study drug
- do not reappear or worsen when dosing with study drug is resumed
- are not a suspected response to the study drug based upon preclinical data or prior clinical data

Yes:

- could not be explained by environmental factors or other treatment(s) being administered
- could not be explained by the patient's disease state or clinical condition
- follow a reasonable temporal sequence following the time of administration of the dose of study drug
- resolve or improve after interruption or discontinuation of study drug
- reappear or worsen when dosing with study drug is resumed
- are known or suspected to be a response to the study drug based upon preclinical data or prior clinical data

Causality to adjuvant surgery:

- Related:
 - The AE follows a reasonable temporal sequence from a protocol specified procedure and cannot be reasonably explained by the nature of the reaction, patient's clinical (eg, disease under study, concurrent diseases, concomitant medications), or other external factors.
- Not Related:
 - The AE does not follow a reasonable sequence from a protocol specified procedure or can be reasonably explained by the nature of the reaction, patient's clinical state (eg, disease under study, concurrent diseases, and concomitant medications) or other external factors.

10.6. Safety Monitoring

The investigator will monitor the safety of study patient at his/her site(s) as per the requirements of this protocol and consistent with current Good Clinical Practice (GCP). Any questions or concerns should be discussed with the sponsor in a timely fashion. The sponsor will monitor the safety data from across all study sites. The Medical/Study Director will have primary responsibility for the emerging safety profile of the compound, but will be supported by other departments (eg, Pharmacovigilance and Risk Management; Biostatistics and Data Management). Safety monitoring will be performed on an ongoing basis (eg, individual review of SAEs) and on a periodic cumulative aggregate basis.

10.7. Investigator Alert Notification

Regeneron (or designee) will inform all investigators participating in this clinical trial, as well as in any other clinical trial using the same investigational drug, of any SAE that meets the relevant requirements for expedited reporting (an AE that is serious, unexpected based on the reference safety information in the IB and has a reasonable suspected causal relationship to the study drug).

11. STATISTICAL PLAN

This section provides the basis for the statistical analysis plan (SAP) for the study. The SAP may be revised during the study to accommodate amendments to the clinical study protocol and to make changes to adapt to unexpected issues in study execution and data that may affect the planned analyses. The final SAP will be issued before the first database lock.

The primary analysis will be performed when all patients have completed surgery or deemed no longer a candidate for surgery after treatment with neoadjuvant cemiplimab. An updated analysis will be provided after all patients have completed post-treatment follow-up or end of study.

Endpoints are listed in Section 4. Analysis variables are listed in Section 5.

11.1. Statistical Hypothesis

The primary endpoint is pCR by independent central review. The following null and alternative hypotheses will be tested for the primary efficacy endpoint:

- H0: pCR rate = 25%
- Ha: pCR rate \neq 25%

11.2. Justification of Sample Size

Seventy-two (72) patients will be required to provide 90% power to reject a null hypothesis of a pCR rate of 25% at a 2-sided significance level of 0.05 if the true pCR rate is 44%.

The sample size will be further increased by 5% to account for patients who prematurely withdraw from the study. Hence, the total sample size will be approximately 76 patients. Patients who discontinue treatment early and/or withdraw from the study will not be replaced. Results will be analyzed according to intention-to-treat. The 95% binomial exact confidence intervals for observed pCR with 76 patients is provided in [Table 6](#).

The non-clinically meaningful pCR rate of 25% will be excluded using the lower limit of 95% exact CI if the observed pCR rate is 36.8% or more.

Table 6: The 95% Binomial Exact Confidence Intervals for Observed pCR with a Sample Size of 76 Patients

Number of pCR patients	Observed pCR rate	95%CI – lower	95% CI – upper
23	0.303	0.202	0.419
24	0.316	0.214	0.433
25	0.329	0.225	0.446
26	0.342	0.237	0.460
27	0.355	0.249	0.473
28	0.368	0.261	0.487
29	0.382	0.272	0.500
30	0.395	0.284	0.514
31	0.408	0.296	0.527
32	0.421	0.309	0.540
33	0.434	0.321	0.553

To ensure meaningful representation of stage III/IV (M0) patients, enrollment of stage II patients will be capped at 25 patients.

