2.2. Sample Size and Power Considerations

Seventy-two (72) patients will be required to provide 90% power to reject a null hypothesis of a pCR rate of 25% at a 2-sided significance level of 0.05 if the true pCR rate is 44%.

The sample size will be further increased by 5% to account for patients who prematurely withdraw from the study. Hence, the total sample size will be approximately 76 patients. Patients who discontinue treatment early and/or withdraw from the study will not be replaced. The 95% binomial exact confidence intervals for observed pCR with 76 patients is provided in [Table 1](#).

The non-clinically meaningful pCR rate of 25% will be excluded using the lower limit of 95% exact CI if the observed pCR rate is 36.8% or more.

Table 1: The 95% Binomial Exact Confidence Intervals for Observed pCR with a Sample Size of 76 Patients

Number of pCR patients	Observed pCR rate	95% CI – lower	95% CI – upper
23	0.303	0.202	0.419
24	0.316	0.214	0.433
25	0.329	0.225	0.446
26	0.342	0.237	0.460
27	0.355	0.249	0.473
28	0.368	0.261	0.487
29	0.382	0.272	0.500
30	0.395	0.284	0.514
31	0.408	0.296	0.527

Number of pCR patients	Observed pCR rate	95%CI – lower	95% CI – upper
32	0.421	0.309	0.540
33	0.434	0.321	0.553

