6.3. Data Handling Convention for Missing Data

No missing data imputation is planned in this study unless specified otherwise.

For categorical variables, patients with missing data are not included in calculations of percentages unless otherwise specified. When relevant, the number of patients with missing data is presented.

Medication missing/partial dates

To determine whether a medication is prior, concomitant or post-treatment medication, the missing medication start date is estimated as early as possible up to date of the first study treatment, and the missing medication end date is estimated as late as possible. If the medication start date is missing, the onset day will not be imputed in medication listings.

Date of first / last study treatment

Date of first infusion is the first non-missing start date of dosing filled in the CRF “Investigational Product” module.

AE suspected to be caused by cemiplimab

If AE suspected to be caused by cemiplimab is missing, the AE relationship will be imputed as related.

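### The 5% inflation to 76 protects the stated 90% power only if withdrawals leave the denominator; kept in as non-pCR, four such patients bring exact power to about 84%, and neither document states how they are scored

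*Protocol*

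**What the plan says.** Protocol 11.2 and SAP 2.2 give the same sizing. Both say "Seventy-two (72) patients will be required to provide 90% power" against a null pCR rate of 25%, with two-sided alpha 0.05 and a true rate of 44%. Then comes the allowance: "The sample size will be further increased by 5% to account for patients who prematurely withdraw from the study". The outcome is "Hence, the total sample size will be approximately 76 patients".

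Protocol 11.2 adds two rules: "Patients who discontinue treatment early and/or withdraw from the study will not be replaced" and "Results will be analyzed according to intention-to-treat". SAP 2.2 keeps the first and omits the second. Both documents put the success bar at an observed rate of 36.8%, which in the accompanying table is 28 of 76.

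The denominator is defined differently in the two documents. Protocol 11.4.1 puts every enrolled patient in the full analysis set (FAS). SAP 3.1 requires at least one dose, and SAP 1.2.4 declares this as a change from the protocol.

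Both documents define pCR by the surgical specimen (Protocol 5.2.1, SAP 4.4.1). SAP 5.6.1 specifies a Clopper-Pearson interval for the primary endpoint and says nothing about patients with no specimen. The general convention in SAP 6.3 for categorical variables is that "patients with missing data are not included in calculations of percentages unless otherwise specified".

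**The concern.** Inflating a sample for dropout assumes that the dropouts leave and that the planned number remains for analysis. Under intention-to-treat they do not leave. A patient lost before surgery cannot be a pCR but still sits in the 76, so the observed rate is diluted while the bar stays at 28. The inflation step and the analysis principle therefore do not fit together.

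Two things are at stake. One is whether the stated 90% describes the design. The other is the primary result itself: if the scoring of treated patients without pathology is left open, the same number of pCRs can pass or fail depending on which sentence the analyst follows. Such patients are foreseen, because Protocol 11 and SAP 5 time the primary analysis to include patients judged no longer candidates for surgery.

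**Working it through.** **Inputs.** Null rate 0.25, alternative 0.44, two-sided alpha 0.05, power 0.90, N = 72, 5% allowance, N = 76, bar 28/76 (Protocol 11.2, SAP 2.2). Analysis by Clopper-Pearson lower limit above 0.25 (Protocol 11.2 and 11.5.3.1, SAP 5.6.1).

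**1. Reproducing the plan's figures.** The documents do not name the sizing formula. The normal approximation with the variance under the alternative gives N = (1.960 + 1.282)² × 0.44 × 0.56 / 0.19² = 71.7, so 72. Then 72 × 1.05 = 75.6 and 72 / 0.95 = 75.8; both round up to 76. The exact lower limit is 0.249 at 27/76 and 0.261 at 28/76, as in the plan's table, so the bar is 28.

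**2. Losses kept in the denominator as non-pCR.** Take 44% as the rate among operated patients and let w dosed patients have no specimen. Success needs 28 pCRs from 76 − w patients, so power = P(Bin(76 − w, 0.44) ≥ 28).

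| w | Exact power |
|---|---|
| 0 | 91.6% |
| 1 | 90.0% |
| 2 | 88.2% |
| 3 | 86.2% |
| 4 | 83.9% |

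The plan's own 5% of 76 is 3.8, about 4 patients. Spreading the loss as a rate gives 0.44 × 0.95 = 0.418, and P(Bin(76, 0.418) ≥ 28) = 84.0%, the same answer.

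**3. 44% as the rate in all analysed patients.** Power at 76 is P(Bin(76, 0.44) ≥ 28) = 91.6%. No inflation would then be needed for non-pCR losses, because they are already inside the 44%.

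**4. SAP FAS, with one loss before dosing.** The undosed patient drops out, leaving n = 75. The lower limit is 0.240 at 26/75 and 0.252 at 27/75, so the bar is 27. With the other three losses counted as non-pCR, 72 patients can respond: P(Bin(72, 0.44) ≥ 27) = 89.1%.

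**5. SAP 6.3 applied literally to four dosed patients without pathology.** They leave the percentage, so n = 72. The lower limit is 0.239 at 25/72 and 0.251 at 26/72, so the bar is 26, and P(Bin(72, 0.44) ≥ 26) = 93.0%.

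**6. Effect on the decision, with four specimens missing.**

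| pCRs | Over 76: rate, lower limit | Over 72: rate, lower limit |
|---|---|---|
| 26 | 34.2%, 0.237 (fail) | 36.1%, 0.251 (pass) |
| 27 | 35.5%, 0.249 (fail) | 37.5%, 0.264 (pass) |

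The gap between the two rules is 93.0 − 83.9 = 9.1 percentage points: the chance, at a true 44% among the 72, of a count on which they disagree. Note that 26/72 would pass at 36.1%, below the 36.8% that both documents give as the bar.

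**The case against.** A reader might infer that the sample size arithmetic is wrong, or that the true power is simply 84%. The documents support neither. The 72, the 76 and the 28/76 bar all reproduce. Reaching 84% takes four conditions together.

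- **44% must be the rate among operated patients.** Protocol 11.2 speaks only of the true pCR rate. If that means all patients, power is 91.6%, above what is claimed. The existence of an inflation step suggests the operated-patient reading but does not prove it.
- **All four losses must fall before surgery.** The allowance is for withdrawal from a study with about 4 years and 3 months of assessment (Protocol 4), and a withdrawal after surgery costs no pCR data. Patients who stop neoadjuvant drug for progression or toxicity are still directed to surgery (Protocol 8.3.5; where clinically appropriate, 9.1.5.1). In the pilot study all 20 patients were operated on (Protocol 3.2.2), though after two doses rather than up to four.
- **All four must have been dosed**, given the SAP's FAS. One pre-dose loss moves the figure to 89.1%, partly because the bar falls in whole patients.
- **They must count as non-pCR.** That is the natural consequence of intention-to-treat and a specimen-based definition, but neither document writes it down.

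A reader might also infer that the SAP definitely drops these patients. It does not go that far: SAP 6.3 yields where something else is specified, and SAP 5.6 places efficacy on the FAS, which can be read as keeping them in.

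These points make the size conditional. They do not remove the mismatch: the 5% gives no protection against losses that stay in the denominator, and the scoring rule for the primary endpoint is absent.

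**Conclusion.** The concern holds in conditional form. Adding 5% preserves 90% power only if withdrawals leave the denominator, and the protocol's intention-to-treat rule, lack of replacement and 28/76 bar keep them in. With 44% as the operated-patient rate and unscored patients taken as non-pCR, the stated 90% survives one such patient and falls to 83.9% at the plan's full allowance of four, all lost after dosing and before surgery. With 44% as the rate in all analysed patients, the claim is met at 91.6%.

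The more consequential part is the missing rule. Across the readings of the allowance worked above, power runs from about 84% to 93%, and with four specimens missing a result of 26 or 27 pCRs depends on an unstated choice of denominator. This is a gap in specification and in the description of power. It does not invalidate the design.

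**What to change.** No extra patients and no change to the 28/76 bar are needed.

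1. In SAP 5.6.1, state that the denominator is every patient in the FAS (all dosed patients), that a patient with no central pathology result counts as non-pCR, and that the SAP 6.3 convention does not apply to this endpoint. Do this before database lock.
2. In Protocol 11.2 (with its synopsis counterpart) and SAP 2.2, restate power along these lines: *Exact power with 76 treated patients and at least 28 pCRs is 91.6% if 44% is the rate in all treated patients, and about 84% if 44% is the rate among operated patients and 5% of treated patients have no specimen.* The wording says treated because the SAP's FAS is dosed patients, whereas 76 in the plan is the number enrolled; if fewer are dosed, the bar has to be recalculated for that number.

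The cost is wording only. The downside is that the stated power looks less favourable under one of the two readings.
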